720 newly diagnosed T2DM subjects (less than 2 years) in good general health as determined by physical exam, medical history, blood chemistries, CBC, TSH/free T4/total T4, lipid profile, urinalysis, and EKG will take part in the study. Subjects must have a HbA_{1c} > 6.5% and must not have taken any oral or injectable antidiabetic medication for more than 2 days, except metformin, and must not be taking any medications known to affect glucose homeostasis. Only subjects whose body weight has been stable (\pm 3lbs) over the preceding three months and who do not participate in an excessively heavy exercise program will be included. Individuals with evidence of proliferative diabetic retinopathy, albuminuria >300 mg/dl, symptomatic diabetic neuropathy, or history of cardiovascular disease (class III-IV CHF) will be excluded. Subjects with AST or ALT greater than 3.5-fold above the upper limit of normal will be excluded. All subjects must be GAD antibody negative. Subjects meeting these criteria will meet with a dietitian and be instructed in a weight maintaining diet containing 50% carbohydrate, 30% fat, and 20% protein. They also will receive instructions about a modest intensity exercise program (40 minutes of walking 3-4 times per week). After one week on the diet, all subjects will receive: (1) oral glucose tolerance test; (2) hyperglycemic clamp-will be performed in a subgroup of 50 subjects (25 in each group) to provide a measure of beta cell function; (3) DEXA for total body fat content/fat distribution; (4) carotid ultrasound-for measurement in carotid intima media thickness; (5) fundus examination; (6) 24-hour urine for albumin and creatinine; (7) ankle arm blood pressure measurement.

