
1) Subjects with type 2 diabetes diagnosed in the past 2 years 2) subjects must be on diet or metformin only 3) age 18-75 years 4) must be in general good health and without a major organ disease 5) must have creatinine < 1.5 6) must have LFT < twice the upper normal limit 7) subjects must have HbA1c > 6.5%
	
(2)	Identify the criteria for exclusion:

1) subjects with type 1 diabetes or positive for anti diabetic antibodies 2) subjects with type 2 diabetes who were diagnosed more than 2 years or who receive insulin or pharmacological therapy other than metformin 3) subjects with a cardiovascular event in the past year
	
(3)	
Recruitment Describe plans how the population will be identified for the purpose of recruiting. (Consider HIPAA Waiver if needed to allow those without existing legitimate access to PHI to use it to identify potential subjects.) (e.g., database search, personal contacts, referrals, patients under the care research team, etc.)

Advertising material will be posted in the medical center and near by hospitals or in primary care offices (advertising material is included for IRB approval). Subjects interested in participating in the study will be asked to contact one of the investigators. We also have access to TDI patient database that can search and select patients that are newly diagnosed diabetic patients or have diabetes markers such as HbA1c . We are planning on identifying such potential subjects and then contacting their health care providers for referral. We will send out "dear Doctor" letter informing the providers about our research study and ask them to contact participants. The treating physician will be making the initial patient contact, not the researcher. If the patient is interested, then either the patient will contact the PI or, with the permission of the patient, the PI will be invited to talk with the patient about study participation.
	
(4)	
Recruitment Describe how initial contact will be made with potential subjects. Describe how those making initial contact have a legitimate access to the subjects' identity and the subjects' information. (Consider HIPAA Waiver if needed to disclose PHI to individuals who would not have otherwise had legitimate access.)

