Type 2 diabetes mellitus (T2DM) is a common metabolic disease that affects 21 million Americans and is associated with significant morbidity and mortality secondary to micro- and macrovascular complications. Subjects with T2DM manifest insulin resistance in skeletal muscle, liver and adipocytes and impaired insulin secretion. Although many therapeutic agents have been developed to target the pathogenic abnormalities in subjects with T2DM, the current ADA recommendation for pharmacological therapy in T2DM remains based on monotherapy, with dose escalation, followed by sequential addition of oral antidiabetic agents and eventually insulin to control blood glucose levels. Unfortunately, the majority of type 2 diabetic individuals in the US fail to achieve the recommended level of glycemic control ($\text{HbA}_{1c} < 6.0\%$) using this approach. In this study, I propose to explore the efficacy of a novel therapeutic approach to attain glycemic control in T2DM subjects. This novel approach is based upon the initiation of triple combination therapy at the time of diagnosis with agents that target specific pathogenic abnormalities present in T2DM. Two groups of newly diagnosed, drug naive T2DM subjects will be studied: (i) Group I will receive triple combination therapy with metformin, pioglitazone, and exenatide as initial therapy; (ii) Group II will be started on metformin monotherapy followed by sequential addition of a sulfonylurea and then glargin insulin. The goal of therapy in both groups is to reduce the $\text{HbA}_{1c} < 6.0\%$. Subjects will be recruited over one year and followed for 2 years (total study duration =3 years). The primary outcome will be the difference in HbA_{1c} between Groups I and II. Secondary outcomes will include failure to achieve the glycemic goal ($\text{HbA}_{1c} < 6.0\%$), improvements in insulin resistance, beta cell function, markers of inflammation, markers of oxidative stress, and carotid intima media thickness. I hypothesize that subjects started on combination therapy at the time of diagnosis of T2DM will have better and more durable glycemic control, a lower rate of therapeutic failure, enhanced insulin sensitivity, and improved/preservation of beta cell function compared to subjects receiving the “conventional” ADA-recommended stepped-therapeutic approach with “standard” medications. I also hypothesize that subjects started on initial combination therapy will have: (i) lower levels of inflammatory markers and (ii) reduced carotid IMT. On a long-term basis, one would expect the superior metabolic control in T2DM who receive aggressive combination therapy from onset to have a lower rate of diabetic complications.

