
The results of this study will provide a novel, more progressive therapeutic approach to the treatment of T2DM, based upon correction of known pathogenic abnormalities responsible for the disease.

Data Analysis and Statistical Methods

Values are presented as mean \pm SEM. Two-sided t test was used to compare mean differences between treatment arms, and the χ^2 test was used to test the significance of discrete variables. The Cox proportional hazards model was used to estimate the influence of therapy on failure to maintain the treatment goal. The model was adjusted for other confounders (namely, age, sex, BMI, disease duration, and baseline HbA1c level).

Sample size calculation:

The study was powered to detect a 0.5% (60.95 SD) HbA1c difference between the two treatment arms based on the HbA1c decrease in the PROactive study (22). We calculated that 76 patients who completed the study would be required in each arm to detect significant difference between the two groups at $\alpha = 0.05$. A detailed description of the sample size

calculation is given in the Supplementary Material.

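### The Abstract's drug-naive, at-diagnosis population is not the one the eligibility criteria admit, and no listed analysis adjusts for prior metformin (minor)

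*Combined protocol and SAP*

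**What the plan says.** **Population in the summary.** The Abstract states: "Two groups of newly diagnosed, drug naive T2DM subjects will be studied". It rests the approach on "initiation of triple combination therapy at the time of diagnosis". Section 1 (hypothesis) and the end of Section 2 (Background) also place the start of therapy at diagnosis.

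**Population in the eligibility text.** Section 3 (Subjects) describes "720 newly diagnosed T2DM subjects (less than 2 years" since diagnosis) who "must not have taken any oral or injectable antidiabetic medication for more than 2 days, except metformin". Section 4, item (1), lists "Subjects with type 2 diabetes diagnosed in the past 2 years" and "subjects must be on diet or metformin only". Section 4, item (2), excludes subjects "who receive insulin or pharmacological therapy other than metformin". These statements agree with one another. Section 3 describes a week on a set diet before the baseline tests but no withdrawal of metformin.

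**Treatment and allocation.** Both arms contain metformin from the start (Section 6a). Allocation is by a table of random numbers, with no stratification factor named.

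**Analysis.** Data Analysis and Statistical Methods gives a two-sided t test for differences in means, a chi-square test, and a Cox model for failure to maintain the goal. Of the Cox model it says: "The model was adjusted for other confounders (namely, age, sex, BMI, disease duration, and baseline HbA1c level"). Prior metformin is not a covariate, stratification factor or subgroup in any listed analysis.

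**The concern.** A subject 20 months from diagnosis whose HbA1c exceeds 6.5% on metformin is eligible, yet is neither drug naive nor at diagnosis. A report that repeats the Abstract's description would attach the result to a population that the trial did not restrict itself to. The novelty claim in Section 2 rests on that description.

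There is also an analysis consequence. The Background puts metformin's HbA1c reduction at about 1.5% and says its efficacy wanes. An entry HbA1c of, say, 7.5% on metformin and the same value on diet alone therefore need not reflect the same underlying disease. Neither baseline HbA1c nor disease duration, both already in the Cox model, fully stands in for prior metformin, because two subjects can match on both and differ in drug exposure. Prior metformin has to be established to judge eligibility, so it is known before randomisation and costs nothing to use. What is at stake is precision, correction of chance imbalance, and the accuracy of the stated population.

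**Working it through.** **1. The plan's own figure.** Inputs from Sample size calculation: difference 0.5, SD 0.95 (the printed 60.95 read as a garbled ±0.95), alpha 0.05. Power is not stated.

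n per arm = 2 × (1.960 + 1.282)² × 0.95² / 0.5² = 75.9, so 76. This is two-sided with 90% power. Two-sided 80% gives 57 and two-sided 95% gives 94. The stated 76 per arm stands and is not in question here.

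**2. Variance explained by prior metformin.** The documents give neither input, so both are assumptions: share on metformin p = 0.20-0.50, shift in final HbA1c d = 0.3-0.7 points.

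R² = p(1−p)d² / 0.95²
- p = 0.2, d = 0.3: 0.16 × 0.09 / 0.9025 = 0.016
- p = 0.5, d = 0.7: 0.25 × 0.49 / 0.9025 = 0.136

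The residual SD, 0.95 × √(1−R²), is then 0.942 to 0.883. The n for 90% power falls from 75.9 to 75.9 × (1−R²) = 74.7 to 65.6, that is 75 to 66 per arm. Power at 76 per arm rises from 0.90 to 0.905-0.937. All of this is against a model with no covariates. The increment over baseline HbA1c cannot be computed from the documents.

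**3. Chance imbalance.** The 1.96-SD range of the between-arm difference in share is 1.96 × √(2p(1−p)/n).
- n = 76: 0.127 (p = 0.2) to 0.159 (p = 0.5). Times d, this moves the HbA1c difference by 0.127 × 0.3 = 0.04 to 0.159 × 0.7 = 0.11 points.
- n = 300 (half of the 600 completers in Section 4): 0.064 to 0.080, or 0.02 to 0.06 points.

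This is already part of the t test's sampling error. The 95% half-width at 76 per arm is 1.96 × 0.95 × √(2/76) = 0.30. The test stays valid; adjustment removes a component that need not be there.

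**4. Cox model.** Simulation with 600 subjects over 3 years, baseline hazard 0.25 per year, true hazard ratio 0.60, 300 replicates. All of these settings are assumed except the 600.
- p = 0.3, prior-metformin hazard ratio 1.5: mean hazard ratio 0.603 without prior metformin, 0.601 with it.
- p = 0.5, prior-metformin hazard ratio 2.5: 0.620 without, 0.595 with; the mean z rises from 4.48 to 4.85.

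Against the true 0.60, the unadjusted estimate is 0.003 to 0.020 too high. At prior-metformin hazard ratio 1.5 and p = 0.2-0.5, the mean z rises by only 0.03-0.06. These runs compare arm alone with arm plus prior metformin, not with the planned five-covariate model.

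**5. What a comparison by prior metformin could show.** The standard error of the difference between the two arm effects is 0.95 × √(2/(np) + 2/(n(1−p))). At n = 76 it is 0.385 (p = 0.2) to 0.308 (p = 0.5), so power to detect a 0.5-point interaction is 0.25-0.37. At n = 300 it is 0.73-0.90.

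**The case against.** The best case for leaving the plan alone has four parts.

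- **The wording is a slip in a summary.** The eligibility statements agree, so nobody screening patients would be misled, and Section 3 itself explains newly diagnosed as less than 2 years. This largely stands. Only the drug-naive label is flatly contradicted; the at-diagnosis wording is loose. Both still need correcting, because the conclusion will be drawn in those words.
- **Part of the adjustment already exists.** Disease duration and baseline HbA1c are Cox covariates. That stands, so the gap in the Cox model is prior metformin alone. It does not help the t test, which has no covariates.
- **The gains may be small.** Both arms contain metformin and are titrated toward the same HbA1c goal, which could shrink any difference by prior use. In the simulations, power was 97% or more with or without adjustment. At 300 per arm, power for the HbA1c difference exceeds 0.999. This stands: no decision is likely to turn on the covariate.
- **The analysis section is written in the past tense**, so a subgroup table added now may be post hoc. That is a reason to label it descriptive.

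A reader might infer two stronger things. One is that omitting prior metformin biases the treatment comparison. It does not in expectation for the HbA1c difference, because treatment is randomised; for the hazard ratio there is only the slight attenuation shown. The other is that the arm effect differs between metformin users and diet-only subjects. Group II's first step is a new drug only for the latter, so this is possible. But metformin in Group I is not new to prior users either, and the documents give no stratum-specific effect.

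**Conclusion.** The point holds as a minor one. The Abstract contradicts the eligibility text on prior treatment and is loose on time since diagnosis. No listed analysis uses prior metformin, although it is known at screening. The HbA1c comparison is unbiased in expectation without it, and 76 per arm is unaffected.

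On assumed inputs (20-50% on metformin, a 0.3-0.7 point shift, SD 0.95), prior metformin explains about 2-14% of HbA1c variance against an empty model. The gain beyond baseline HbA1c will differ and is unknown. Hazard-ratio attenuation is about 0.00-0.02, with the upper end needing half the subjects on metformin and a prior-metformin hazard ratio of 2.5.

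Confidence is high on the contradiction and the omission, and low on the size of any gain. The Supplementary Material cited for the sample size is not among the documents.

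**What to change.** 1. Analyse HbA1c with a linear model containing arm, baseline HbA1c and prior metformin (yes/no), and report the adjusted difference with its confidence interval.
2. Add prior metformin to the five Cox covariates.
3. Report the arm effect with confidence intervals by prior metformin, labelled descriptive, since interaction power is only 0.25-0.37 at 76 per arm. If outcome data have already been seen when this is added, say so.
4. Reconcile the population wording in Section 1, the end of Section 2 and the Abstract with the eligibility text in Sections 3 and 4, so that it reads as within 2 years of diagnosis, on diet or metformin.

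The cost is one extra covariate in each model, one descriptive table and a wording edit. No extra patients or visits are needed, and the eligibility check already has to establish prior metformin use.

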Following completion of these tests, subjects will be randomized (using a table of random numbers) to receive, in open label fashion, one of the following treatment regimens: (i) Group I will be started on pioglitazone (15 mg/day) plus metformin (1000 mg/day) with the supper meal and exenatide (5 mcg s.c. bid 30 min before breakfast and supper) and up-titrated to 45 pioglitazone plus 2000 metformin and 10 mcg s.c. bid exenatide to achieve HbA1c <6.0%; (II) Group II will be started on metformin, 1000 mg with breakfast and 1000 mg with supper, glyburide and basal insulin will be added and up titrated to achieve HbA1c <6.0% Subjects will be recruited during the first year and followed up for additional two years. After completing the repeat studies, subjects will be asked to continue in the study and with the study medications without any change. Follow up visits will occur every 3 months) until the last patient recruited into the study completes 2 –years of follow-up. At the Follow visit Fasting Glucose and HbA1C will be performed. At the annual visits blood work to check the following: fasting glucose, HbA1C, and other repeat labs. Every 2 years or if the subject decides to discontinue participation, we will repeat the annual labs, OGTT, eye photographs, and carotid ultrasound.

4. Study Population(s).

You will be drawing subjects from one or more populations. In medical research, for example, a population can be individuals with type 2 diabetes controlled with diet, or a population of healthy individuals. In social behavioral research, a population can be individuals attending an education program, etc.

- a. How many different populations are you enrolling in this study?
- b. For each different population, provide a short descriptive label: (e.g., *normal-healthy, diabetics, patients needing surgery, parents, child, etc.*)

1

720 Newly diagnosed type 2 diabetic subjects
Will be enrolled to have 600 completers .

For each **specific** population identified 4b, provide the following information in the table provided below. (**One table is provided, use copy and paste for additional tables if enrolling more than one population.**)

Population # [Type # given to population in 4b]	Population Descriptive Label: [Insert short label from 4b] Enrollment of [Insert #] requested to obtain [Insert #] completers.
XCheck here if enrolling only one population	
(1)	Identify the criteria for inclusion :

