If, after month six, the HbA_{1C} $> 6.0\%$, and the subject is on maximum doses of metformin, glipizide, and glargine insulin, the subject will be considered a treatment failure. Regular insulin will be added to each meal when the HbA_{1C} rises to $> 6.5\%$ and adjusted based upon the pre- and post-meal blood glucose levels. These "treatment failure" subjects will continue with all follow up visits/procedures.

Throughout the titration process, downward adjustments will be allowed for the development of hypoglycemia, as defined by a blood glucose less than 60 mg/dl with (symptomatic hypoglycemia) or without (asymptomatic hypoglycemia) symptoms. Serious hypoglycemia is defined as any hypoglycemic reaction requiring assistance from a third party for recovery.

Following their enrollment into the study, all T2DM participants will return to the Clinical Research Center (CRC) at the TDI for follow up visits every 3 months. Telephone calls also will be made to each participant every 6 weeks. During the telephone/CRC visits, subjects will be asked questions about interim medical history, home glucose monitoring results, and compliance with the medical regimen.

During each 3-month follow-up visit to the CRC, body weight, waist circumference (Gulick III tape measure), and blood pressure (Dynamap) will be measured. Blood will be drawn for FPG and HbA_{1c}, and pharmacological therapy will be adjusted based on the HbA_{1c}, FPG, and HBGM results (see prior algorithm). Plasma lipids and 24-hour urine albumin excretion will be measured annually or more frequently as indicated by test results. In addition to glycemic control, all subjects will receive therapy for any abnormal cardiovascular risk factors: hypercholesterolemia (goal LDL <100 mg/dl), hypertriglyceridemia (goal <150 mg/dl), hypertension (goal <130/80 monthly), albumin excretion (goal < 30 mg/day). At the end of three years, the OGTT, DEXA, fundus photography, 24 hour urine for albumin, hyperglycemic clamp, ankle-arm blood pressure, and carotid IMT will be repeated.

Primary End Point: The primary end point of the study is the difference in HbA_{1c} between Group I (triple combination therapy at time of initial diagnosis) and Group II (stepwise therapy).

Secondary End Points: The following parameters will be measured as secondary endpoints;

- 1) Number of subjects in each group with HbA_{1c} < 6.0%

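### The only stated method that fits the primary HbA1c endpoint is a t test with no covariate, no named visit and no stated handling of subjects sent back to their own doctor

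*Combined protocol and SAP*

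**What the plan says.** Section 6a states that "The primary end point of the study is the difference in HbA_{1c} between Group I" and Group II. The Abstract agrees: "The primary outcome will be the difference in HbA_{1c} between Groups I and II". Neither names a visit or mentions change from baseline.

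Data Analysis and Statistical Methods lists three methods: a t test for means, a chi-square test for discrete variables, and a Cox model for failure to maintain the treatment goal. The t test sentence reads "Two-sided t test was used to compare mean differences between treatment arms". Covariates appear only with the Cox model: "The model was adjusted for other confounders (namely, age, sex, BMI, disease duration, and baseline HbA1c level").

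HbA1c is available far more often than a single comparison needs. At each 3-month visit, "Blood will be drawn for FPG and HbA_{1c}, and pharmacological therapy will be adjusted" (Section 6a).

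The trial is sized in completers. Under Sample size calculation, "We calculated that 76 patients who completed the study would be required in each arm"; in Section 4, the 720 subjects "Will be enrolled to have 600 completers". No analysis set and no rule for missing HbA1c is given.

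On subjects who do badly, Section 6a keeps treatment failures in both groups on the full follow-up schedule. Section 7, item 7, classes full-dose subjects whose A1c stays above 8% as treatment failures and sends them back to their own physician. Section 3 schedules repeat tests every 2 years, or "if the subject decides to discontinue participation, we will repeat the annual labs". It names no blood draw for a return under Section 7.

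**The concern.** There are two separate matters.

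The first is efficiency. Baseline HbA1c must be known for eligibility and already adjusts the Cox model. The quarterly values are already planned. A primary comparison that names no covariate and no longitudinal model may leave this information unused.

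The second is possible selection on the outcome. A return under Section 7 is triggered by high HbA1c, which is the primary variable. If it ends HbA1c collection, and the analysis then uses only subjects who finish, the highest values leave the comparison. The number leaving each arm would depend on treatment. Randomisation no longer protects such a comparison, and covariates in a completers-only t test would not in general repair it. The plan neither says that this will happen nor rules it out.

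**Working it through.** **1. The plan's own figure.** Inputs from Sample size calculation: difference 0.5, two-sided alpha 0.05, and SD 0.95 (the printed 60.95 is read as a plus-minus sign lost in conversion). Power is not stated in the available text; 90% is inferred because it fits.

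n per arm = 2 × (1.960 + 1.282)² × 0.95² / 0.5² = 75.9, rounded up to 76. This matches the plan, so the sample size is consistent with an unadjusted two-sample comparison.

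**2. Gain from baseline adjustment.** Assumptions: a baseline to follow-up correlation r of 0.3 to 0.6, which is not in the documents; equal variance at both times; 300 completers per arm (600 / 2, Section 4).

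Against a t test on final values, the variance is multiplied by 1 − r². The 95% CI half-width is 1.96 × 0.95 × √(2/300) × √(1 − r²):

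| r | variance factor | SE | half-width |
|---|---|---|---|
| 0 (no adjustment) | 1.00 | 0.0776 | 0.152 |
| 0.3 | 0.91 | 0.0740 | 0.145 |
| 0.6 | 0.64 | 0.0621 | 0.122 |

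This is 9% to 36% less variance. Against a t test on change, the ratio is (1 − r²) / (2(1 − r)) = (1 + r)/2, which is 0.65 at r = 0.3 and 0.80 at r = 0.6: 35% to 20% less variance.

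Power for 0.5 at 300 per arm exceeds 99.99%, so power is not the argument here.

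**3. Planned loss.** 720 − 600 = 120, and 120/720 = 16.7%. No rule says how these subjects enter the analysis.

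**4. Illustration of exit on HbA1c.** Only the SD and the visit spacing come from the documents; everything else is assumed. The true difference is set at 0.50.

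*Check by hand.* If everyone above 8% at a single time is dropped, the mean of those left is μ − 0.95 × φ(b)/Φ(b), with b = (8 − μ)/0.95.
- μ = 6.0: 1.8% dropped, mean left 5.958.
- μ = 6.5: 5.7% dropped, mean left 6.384.
- μ = 7.0: 14.6% dropped, mean left 6.745.

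Means 6.0 and 6.5 give 6.384 − 5.958 = 0.43. Means 6.5 and 7.0 give 6.745 − 6.384 = 0.36.

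*Over time.* A simulation used visits every 3 months from month 6 to 36, a between-subject share of variance of 0.6 or 0.8, autoregressive residuals (0.5), exit after two consecutive values above 8%, no response to rescue, and exits left out:

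| share at full dose, each arm | means 6.0 / 6.5 | means 6.5 / 7.0 |
|---|---|---|
| all | 0.40-0.41 | 0.33-0.34 |
| half | 0.46 | 0.43-0.44 |

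With equal full-dose shares, a true 0.50 therefore becomes about 0.33 to 0.46. The direction is not fixed: if only Group I subjects could exit, the same model gives 0.55 to 0.66. These are conditional illustrations and do not forecast the trial.

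**5. The two passages side by side.** Section 6a: treatment failures stay on all visits. Section 7, item 7: a treatment failure above 8% at full dose goes back to the usual physician. Both use the term treatment failure, with different thresholds and different consequences. Section 7 does not say that visits stop, and Section 6a makes no exception for values above 8%.

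**The case against.** The strongest reply is that a t test in a randomised trial is valid and simple, and that with 300 per arm precision is ample. That stands. The adjusted model is better value but does not rescue an invalid test.

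A reader might infer that the test ignores baseline altogether. The documents do not support this. The test is described as comparing mean differences, and the sample size refers to an HbA1c decrease. A t test on change would use baseline by subtraction. What can be said is that no covariate is named and the choice between final value and change is not stated.

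A reader might also infer that the result will be biased. That needs three steps: that Section 7 overrides Section 6a, that return to the usual physician ends HbA1c collection, and that those subjects are left out of the analysis. None is stated. If Section 6a governs, or if visits continue while care is transferred, this bias does not arise.

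Section 3 should not be read as collecting labs only when a subject chooses to stop. Repeat labs also come every 2 years, and annual visits include HbA1c. The gap is narrower: no draw is tied to a return under Section 7.

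Nor do the documents establish that one arm can exit more readily. Group I glargine has a stated 60-unit maximum and Group II basal insulin has none. However, mealtime insulin is added in both arms with no stated maximum, and Section 7 does not define full dose.

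Finally, the simulated figures depend on the chosen inputs. Requiring three high values instead of two moves the result with all subjects at full dose from 0.33-0.41 to 0.36-0.44. This limits what the figures show, but it does not supply the missing rule.

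**Conclusion.** The point holds as an incomplete and improvable specification of the primary analysis and should be fixed. It is not a fatal flaw.

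The efficiency part rests on an assumed correlation and is modest in absolute terms: against a test on final values, at most 0.03 off the CI half-width at 300 per arm (0.152 − 0.122).

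The selection part is conditional. It justifies reconciling the passages and stating the analysis set, but it is not a demonstrated bias. Its size and direction depend on arm means, on who counts as full dose, and on what happens to HbA1c after exit. The documents give none of these. Confidence is medium.

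**What to change.** In the SAP:
- Make the primary analysis a baseline-adjusted repeated-measures model, for example an MMRM with baseline HbA1c, visit, treatment and treatment-by-visit terms. Include all randomised subjects by assigned group and all scheduled HbA1c values, and take the arm contrast at a named primary visit.
- State whether HbA1c after rescue or exit is included. If it is, the target is the difference including rescue and later care, which need not equal the 0.5 used for sizing.
- State that the model is valid if loss depends on observed HbA1c, and add one sensitivity analysis for departures from this.
- Keep the t test as a sensitivity analysis, stating its analysis set and whether it uses final values or change.

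In the protocol:
- Reconcile Section 7, item 7, with the treatment-failure text in Section 6a. Which clinical rule applies is for the investigators.
- State that scheduled HbA1c collection continues to the primary visit, whoever manages care.

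The cost is SAP wording, slightly more analysis work, the reconciled protocol text, and some effort to obtain HbA1c after a return under Section 7. For all other subjects the quarterly measurements are already planned.
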